- (8) Sexually active females of childbearing potential enrolled in the study must agree to use two forms of accepted methods of contraception during the course of the study and for 3 months after their last dose of study drug. Effective birth control includes:
 - Intra-uterine contraceptive device plus 1 barrier method;
 - Stable doses of hormonal contraception (e.g., oral, injectable, subcutaneously implanted, transdermal) for at least 3 months plus 1 barrier method;
 - Two barrier methods. Effective barrier methods are male or female condoms, diaphragms, and spermicides (creams or gels that contain a chemical to kill sperm); or
 - A vasectomized partner.
- (9) For male subjects who are sexually active and who are partners of females of childbearing potential: must agree to use 2 recognized methods of contraception during the treatment period and for 3 months after the last dose of study drug (see criterion 8 above).
- (10) Subject (or the subject's legally authorized representative) must be fully informed of the study contents and is able to provide written ICF prior to any study-specific procedures, and is willing to follow the treatment regimen and visit schedule.

Exclusion Criteria

Subjects who met any of the following conditions would be excluded from the study:

- (1) Received a systemic investigational cGVHD treatment within 28 days of study entry, but prior treatment is allowed with a washout of at least 28 days or 5 half-lives.[Note: Corticosteroids, CNIs, sirolimus, mycophenolate mofetil (MMF), methotrexate, azathioprine, and *in vitro* photochemotherapy (ECP) are acceptable and subjects must have been on a stable dose/regimen of these for at least 2 weeks prior to screening].
- (2) Recurrence of hematologic tumor (according to criteria for recurrence of the corresponding primary hematologic tumor) or post-transplant lymphoproliferative disease at screening.
- (3) Current treatment with ibrutinib (except for ibrutinib with a washout of at least 28 days prior to the first dose of the investigational product).

Laboratory Tests

- (4) Absolute neutrophil count (ANC) $< 1.5 \times 10^9/L$.
- (5) Platelet count $< 50 \times 10^9/L$.
- (6) Alanine aminotransferase (ALT) > 3 × upper limit of normal (ULN), aspartate aminotransferase (AST) > 3 × ULN
- (7) Total bilirubin (TBIL) $> 1.5 \times ULN$.
- (8) Creatinine clearance (CrCl) < 60 mL/min (Cockcroft-Gault formula).

General Criteria

- (9) Pregnant or lactating women.

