- 7) Study drug administration;
- 8) Issuance/retrieval of subject logs;
- 9) Combined medications/treatments (including doses of corticosteroids and other cGVHD treatments);
- 10) AE.

It is up to the investigator to decide whether or not to perform this test based on the subject's condition.

4.3.3 Day 1 of Cycle 2 ~ Cycle N (C2D1 ~ CxD1, time window for the corresponding examination: ±3 days):

Prior to dosing

- 1) Co-medication/treatment (including doses of corticosteroids and other cGVHD treatments);
- 2) AE
- 3) Symptom-directed physical examination;
- 4) Vital signs (including temperature, respiratory rate, sitting blood pressure and pulse);

- 5) Body weight;
- 6) ECOG PS score;
- 7) Blood routine, urine, and blood biochemistry;
- 8) 12-lead electrocardiogram (3 consecutive measurements taken within 60 minutes prior to dosing on Day 1 of Cycle 2 and Cycle 4, each 1 to 2 minutes apart);
- 9) Echocardiogram (LVEF)#;
- 10) Urine pregnancy test (for females of childbearing age only, positive results to be confirmed by serologic testing);
- 11) PK blood collection (within 60 minutes prior to dosing on Cycle 2, Cycle 3 and Cycle 4 Day 1);
- 12) Physician cGVHD activity assessment[†];
- 13) cGVHD response assessment[†];
- 14) Pulmonary function tests† [may also be assessed post-dose; where a complete pulmonary function test including FEV1, FVC, DLCO (corrected for Hb), TLC, and RV is required on Day 1 of Cycle 4, Cycle 7, and every 6 cycles thereafter (e.g., Cycle 13, Cycle 19, as applicable), and on other cycles (e.g., Cycle 2, Cycle 3, Cycle 5, and Cycle 6, etc.), a spirometer test only (including FEV1 and FVC testing) is required];
- 15) Patient-reported cGVHD activity assessment[†];
- 16) Lee Symptom Scale score[†];
- 17) PROMIS Physical-Psychological Functioning Global Health Score[†].
- # The decision to perform this test was made by the investigator on a subject-by-subject basis.

Drug administration and post administration

- 1) Administration of study drug;
- 2) Dispensing/recovery of study drug and subject logs;
- 3) Combined medications/treatments (including doses of corticosteroids and other cGVHD treatments);
- 4) AE;
- 5) 12-lead electrocardiogram [3 consecutive measurements 1.5 hours (± 20 minutes) after dosing on Day 1 of Cycle 2 and Cycle 4 at 1-2 minute intervals; single measurement 1.5 hours (± 20 minutes) after dosing on Cycle 7 and subsequent visits];

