4.3.7 Unscheduled visits

During the study period, the investigator may decide whether to add unscheduled visits based on clinical needs (e.g., clinically significant laboratory test abnormalities, AEs, etc.). During unscheduled visits, the corresponding tests and AEs, etc. should be recorded in the original data and eCRF. If the same test is performed multiple times on the same day, only one set of test values (e.g., the earliest test result of the day) should be recorded in the eCRF, but all abnormal values of repeated tests should be

recorded in the eCRF.

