6.1 Dose Adjustment

Subjects who experience any clinically significant toxicity during treatment will need to be considered for suspension or termination of study drug therapy. Subjects who experience an AE related to study treatment may be dosed according to Table 3.

Table 3 BN101/belumosudil dose adjustment

Toxicity*	Dose Adjustment
≥ grade 3 hepatotoxicity (ALT/AST/TBIL)	 Suspend BN101/belumosudil administration; Within 14 days§toxicity does not return to ≤ Grade 1 or baseline level, then discontinue BN101/belumosudil therapy; Within 14 days§toxicity returns to ≤ Grade 1 or Baseline level, resume BN101/belumosudil administration at a reduced dose level [e.g., 200 mg QD → 200 mg once every other day (QOD)]; If the reduced dose level is administered for one full treatment cycle tolerated by the subject without recurrence of Grade 1 or greater hepatic function abnormality, return the dose to the original level for the following treatment cycle[e.g., 200 mg QOD → 200 mg QD]; If this toxic reaction recurs after the reduced dose level, terminate BN101/belumosudil treatment.
Other ≥ grade 3 clinically significant toxicity associated with BN101/belumosudil	 Suspend BN101/belumosudil administration; Within 14 days§toxicity does not return to ≤ Grade 1 or baseline level, then discontinue BN101/belumosudil therapy; Within 14 days§toxicity returns to ≤ Grade 1 or baseline level, then BN101/belumosudil administration is resumed at a reduced dose level [e.g., 200 mg QD → 200 mg QOD]; if the reduced dose level is administered for a full treatment cycle as tolerated by the subject, and there is no recurrence of Grade 1 or higher of this abnormality, then the next cycle of treatment the dose will be restored to the original level [e.g., 200 mg QOD → 200 mg QD]; If the toxic reaction recurs after administration at a reduced dose level, BN101/belumosudil treatment will be discontinued.

^{*} Severity of toxicity was determined according to NCI CTCAE v5.0.

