6.3 Management of Overdose

An overdose dose of BN101/belumosudil has not been established. In clinical studies of BN101/belumosudil, a 500 mg BID dose of BN101/belumosudil given to healthy volunteers for 28 consecutive days was well tolerated, suggesting that the drug has a wide safety window and that overdose is unlikely. There is no known antidote for BN101/belumosudil and no specific treatment recommendations in case of suspected overdose. Investigators should exercise comprehensive judgment in the management of subjects with suspected overdose based on their clinical condition.

[§]The maximum time allowed for suspension of BN101/belumosudil administration due to toxicity was 14 days, and subjects who discontinued for more than 14 days were required to withdraw from the study. If a subject can tolerate 1 full cycle of treatment after a BN101/belumosudil dose reduction, the dose may be restored to the dose prior to the reduction for the next cycle.

The reporting and management of overdose is detailed in Section 8.9.

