8.6.2 Collection and reporting procedures

8.6.2.1 Adverse Event Collection and Reporting

PTE and AE collection period

Collection of PTE will begin when the subject signs informed consent and continue until the subject first receives study drug or until screening failure. For subjects who withdraw from the study prior to study drug administration, PTE will be collected until the subject withdraws from the study.

Collection of AEs will begin when the subject first receives study drug and continue until 28 ± 7 days after the last dose of study drug or until initiation of new treatment for systemic cGVHD, whichever occurs first, whether or not related to study drug, and must be collected and recorded by the investigator. Only AEs/SAEs related to study treatment were collected and recorded 28 ± 7 days after the last dose of study drug or after initiation of new systemic cGVHD treatment and were required to be followed until the event was resolved and the investigator considered the event to be stabilized or irreversible.

The end date of the PTE/AE was the date when the event was resolved and deemed stable or

irreversible by the investigator.

PTE and AE Reporting

At each study visit, the investigator will assess whether a subjective AE has occurred. A neutral question may be asked, such as "How have you felt since your last visit?" . Subjects may report AEs that occur at any other time during the study.

All PTEs occurring in subjects must be monitored until symptoms subside or until any clinically relevant changes in laboratory tests have returned to baseline, or until a satisfactory explanation for the change has been provided. Non-severe PTEs related or unrelated to study operations are not required to be followed up for study protocol purposes.

All subjects experiencing AEs, whether or not related to study drug use, must be monitored until symptoms have subsided and any clinically relevant changes in laboratory test values have returned to baseline, or until a satisfactory explanation for the observed changes has been provided.

All clinically significant laboratory test abnormalities confirmed by laboratory retesting will be followed until these abnormalities have returned to acceptable levels or have been satisfactorily explained.

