- 9. Virology includes Hepatitis B Surface antigen (HBsAg), Hepatitis B Surface Antibody (HBsAb), Hepatitis B core antibody (HBcAb), Hepatitis Be antigen (HBeAg), Hepatitis Be antibody (HBeAb), Hepatitis C antibody (HCV-Ab), human immunodeficiency virus (HIV) antibody, Hepatitis B virus DNA (HBV-DNA) (if applicable), Hepatitis C virus RNA (HCV-RNA) (if applicable). If they are done at the site within 28 days prior to screening and reports can be provided, the investigator determines that the test can be used as a result of the screening period. When HBcAb or HCV-Ab is positive, HBV-DNA or HCV-RNA should be tested to rule out active infection.
- 10. 12-Lead ECG see ECG Assessment table.
- 11. Female of childbearing age are tested for pregnancy. For this study, the reproductive age was defined as non-menopausal, and menopause included natural amenorrhea ≥12 months; Or natural amenorrhea ≥24 months after chemotherapy; Or natural amenorrhea ≥6 months and serum follicle-stimulating hormone (FSH) level > 40 IU/L; Or confirmed surgical records and/or pathology reports confirmed after bilateral oophorectomy. Serum pregnancy tests for women of childbearing age during the screening period must be negative. Urine pregnancy test can be performed as needed during the study treatment. Positive results are to be confirmed with serum testing. If the urine pregnancy result is positive, subjects should stop the study drug treatment and withdraw from the study, and the investigators will continue to follow up subjects until delivery and 30 days after delivery. Subjects who did not deliver were followed up until the end of the pregnancy.
- 12. On Day 1 of Cycles 1 to 7, subjects will take their dose at the clinic and then will be dispensed study drug for home administration. Instruct subjects to fill in the study drug dairy. From Cycle 8 onwards, the Day 1 dose may be taken at home or in the clinic.

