- 13. The end of the main study is defined as 12 months after the last subject was enrolled. Subjects who have not yet experienced cGVHD progression at the end of the main study, and in the judgment of the investigator, the benefits of continued dosing outweigh the risks, may submit a written request and, upon approval by the sponsor's Medical Director and documentation of the subject's willingness to continue the treatment, the sponsor will continue to provide BN101/belumosudil medication at no cost until cGVHD progression, intolerable toxicity, initiation of a new cGVHD therapy, recurrence of hematological neoplasm, loss to follow-up, withdrawal of consent, or death, etc., whichever occurred first. For subjects assessed as "Lack of Response Mixed" and "Lack of Response Progression" (see the main body of the protocol), if the investigator believed that these subjects could continue to benefit from treatment with BN101/belumosudil, the treatment may be continued after a written application was submitted, and approval from the Sponsor's Medical Director as well as documentation of the subject's willingness to continue treatment was obtained.
- 14. On the first day of cycle 7 (C7D1) and all subsequent odd cycles (C7D1, C9D1, C11D1, etc.), subjects will receive 2 cycles of study drugs and 2 copies of drug dairy and return to the clinic for efficacy and safety assessment every other treatment cycle, as well as dispense/collect study drugs until the end of the main study.
- 15. Subjects will return to the clinic for EOT assessment within 7 days after the final administration of the study drug or at the end of the main study (only for subjects who have not discontinued the study drug at the end of the main study). Subjects who withdraw from the trial early should also return to the clinic for EOT assessment. End-of-treatment visits are also required at the end of the main study if subjects have not discontinued study drug at the end of the main study. EOT

Cycle Day (d)	Screening/Baseline		Cycle 1		Cycle 2~N ^{13,14}	End of Treatment (EOT) ¹⁵	28-Day Follow-Up ¹⁶	Long Term Follow-Up ¹⁷
Assessment	-14 ~ -1	-7 ~ -1	C1D1	C1D8、15 (±3)	CxD1 (±3)	(+7)	(土)	At the end of treatment or at the end of the main study

visits should be done prior to new treatment.

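### Table 3's footnote drops the no-recurrence condition for return to daily dosing, and from Cycle 7 the protocol conflicts on whether a liver test is due at that decision

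*Protocol*

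**What the plan says.** **Dose rule.** Protocol section 6.1, Table 3, suspends drug for a grade 3 or higher ALT, AST or TBIL abnormality. Drug restarts at QOD if the value is back to Grade 1 or lower, or to baseline, within 14 days; otherwise it stops for good. For the step back to QD after one full tolerated QOD cycle, the hepatic row says: "without recurrence of Grade 1 or greater hepatic function abnormality, return the dose to the original level for the following treatment cycle". The row for other grade 3 or higher toxicities carries the same kind of condition. The table's footnote (which appears in the text after section 6.3) and its synopsis copy say: "If a subject can tolerate 1 full cycle of treatment after a BN101/belumosudil dose reduction, the dose may be restored". They mention neither grade nor laboratory result.

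**Schedule.** Section 4.3.3 covers Day 1 of Cycle 2 onward and lists "Blood routine, urine, and blood biochemistry" before dosing. It marks the efficacy items with a dagger for every-other-cycle assessment from Cycle 5; chemistry has no dagger. Appendix 1 note 14, attached to the column for Cycle 2 onward, dispenses two cycles of drug from C7D1 and has patients "return to the clinic for efficacy and safety assessment every other treatment cycle". Note 12 adds: "From Cycle 8 onwards, the Day 1 dose may be taken at home or in the clinic".

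**The concern.** Return to full dose after a grade 3 or higher liver event should rest on one rule and on a liver result. Here the row and the footnote state different conditions for the same step. A raised ALT, AST or bilirubin can be silent, so a patient may be judged to have tolerated a cycle while failing the row's condition.

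The schedule adds to this. If a site follows note 14, the decision can fall on a day with no visit and no scheduled chemistry near it. A site that follows section 4.3.3 would test that day. The stake is patient safety and uniform handling across the planned 6 to 9 centers, not the efficacy estimate.

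**Working it through.** The plan gives no figure to reproduce. The check has two parts.

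**1. Conditions for return from QOD to QD**

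| Place | One full tolerated cycle | No Grade 1 or higher recurrence |
|---|---|---|
| Table 3, hepatic row | required | required |
| Table 3, other-toxicity row | required | required |
| Table 3 footnote | required | not mentioned |
| Synopsis rows | required | required |
| Synopsis footnote | required | not mentioned |

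**2. Timing of the decision against scheduled chemistry**

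Inputs: cycle length 28 days (section 3.3); longest hold 14 days (Table 3 footnote); Day 1 visits with a window of ±3 days (section 4.3.3); visits every other cycle from C7D1 (note 14).

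Day of CkD1 = 28 × (k − 1) + 1. So C6D1 = 141, C7D1 = 169, C8D1 = 197 and C9D1 = 225.

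Assuming cycles stay on the calendar during a hold, a restart in Cycle k makes Cycle k + 1 the full QOD cycle, and return to QD falls on Day 1 of Cycle k + 2. A restart in an even cycle therefore leads to a return on an even cycle's Day 1.

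- **Event found at C6D1 (day 141).** Restart by 141 + 14 = 155, in Cycle 6. The full QOD cycle is Cycle 7 (days 169 to 196). Return to QD is at C8D1, day 197.
  - Under note 14, the nearest scheduled tests are C7D1 (197 − 169 = 28 days before) and C9D1 (225 − 197 = 28 days after). If each of those visits moves by up to 3 days, each gap is 25 to 31 days.
  - Under section 4.3.3, chemistry is due on day 197 itself, before dosing.
- **Event found at C5D1 (day 113).** Restart by day 127, full QOD cycle = Cycle 6, return at C7D1. This is a clinic visit with chemistry.
- **Event found at C7D1 (day 169).** Restart by day 183, full QOD cycle = Cycle 8, return at C9D1. This is also a clinic visit. C9D1 and C11D1 behave the same way.
- **Event found off schedule in a later even cycle, for example day 204 in Cycle 8.** Restart by day 218, full QOD cycle = Cycle 9 (days 225 to 252), return at C10D1 = day 253. The nearest tests under note 14 are days 225 and 281, again 28 days either side.

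In the C6D1 case, the C7D1 test shows the liver values at the start of the full QOD cycle. No scheduled result under note 14 covers the rest of that cycle or its end, which is what the row asks about.

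**The case against.** A reader might infer more than the documents support.

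- **That the footnote overrides the rows.** It is permissive, uses the rows' own notion of tolerance and does not say that recurrence may be ignored, so it can be read as a loose summary. That weakens the charge but does not remove it: the sentence still omits a condition that both rows impose, and tolerance is not defined.
- **That no liver test is required during the hold.** A 14-day rule tied to grade cannot be applied without a test. Section 8.6.2.1 says that subjects with adverse events "must be monitored until symptoms have subsided and any clinically relevant changes in laboratory test values have returned to baseline" or until the change is explained, and section 4.3.7 says that "the investigator may decide whether to add unscheduled visits based on clinical needs". Only a fixed interval is missing, and leaving that to the investigator is a defensible choice.
- **That patients can raise their own dose at home.** Note 12 concerns where the Day 1 dose is taken. Section 5.5 reserves prescribing to the principal investigator or an authorized physician.
- **That many patients are exposed.** Cycle-aligned returns up to C7D1 have scheduled chemistry. Among scheduled visits, only C6D1 leads to a return without a visit; the other routes need off-schedule detection.
- **That a persisting Grade 1 or raised baseline value blocks return to QD.** The row speaks of recurrence, and a value that never cleared has not recurred. Any threshold there is a clinical choice.

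Unscheduled testing by a careful investigator would often close the gap. But neither section 4.3.7 nor section 8.6.2.1 requires a result before return to QD.

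**Conclusion.** Wrong as written: an internal conflict in a safety rule. Two contradictions stand. The Table 3 footnote and its synopsis copy omit the no-recurrence condition in both rows. From Cycle 7, note 14 and section 4.3.3 disagree on chemistry frequency. Together they allow a return-to-QD decision at C8D1, or at a later even-cycle Day 1, with the nearest scheduled liver tests 28 days away on either side.

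This rests on cycles staying on the calendar and on a site following note 14. How many patients would take this path cannot be computed, because the documents give no grade 3 or higher hepatic rate. Protocol Table 1 gives any-grade ALT increase in 10 of 83 (12.0%) at 200 mg QD in cGVHD. If, as an assumption, 1% to 5% had a grade 3 or higher event, that would be 30 × 0.01 = 0.3 to 30 × 0.05 = 1.5 of 30 patients at any time on treatment; those on this path would be fewer. ORR and sample size are not affected.

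**What to change.** 1. Delete the sentence beginning "If a subject can tolerate 1 full cycle of treatment after a BN101/belumosudil dose reduction, the dose may be restored" under Table 3 and in the synopsis, so that the row condition governs.
2. Add to the hepatic row and its synopsis copy: *Do not return to QD without ALT, AST and TBIL results obtained at the end of the full QOD cycle.*
3. Add to Appendix 1 note 14: *Subjects on QOD because of hepatotoxicity (not those tapering off) have chemistry, at the clinic or a local laboratory, on Day 1 of every cycle until QD is restored.* Then align note 14 with section 4.3.3 on chemistry frequency for all patients.

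A fixed retest day during the 14-day hold is an optional clarification. If added, it should fall early enough for the result to be available by Day 14, since a longer hold forces withdrawal.

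The cost is a few text edits and one or a few extra local blood draws per affected patient. In the C6D1 example it is one draw, at C8D1, beyond what note 14 already schedules. If the sponsor settles on chemistry every cycle for everyone, that is what section 4.3.3 already lists.

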6.2 Management of Missed Doses

Subjects should endeavor to take the study drug at the same time each day as prescribed by the protocol.

If vomiting occurs after taking BN101/belumosudil and an insufficient dose of study drug is administered, no make-up dose is required. It is sufficient to continue to take the prescribed dose the following day.

Subjects who noticed a missed dose of study medication were allowed to take one make-up dose of the current dose if it was more than 12 hours before the next dose and still take the prescribed dose on the following day; if it was less than 12 hours before the next dose, there was no make-up dose of the current medication, and the dose was still taken on the following day.

